6. STATISTICAL CONSIDERATIONS AND ANALYSIS PLAN

Database lock to enable the analysis of the 6-week treatment phase of the study will occur once all subjects have either completed the 6-week assessments or withdrawn from the study early, and all data required for analysis have been cleaned and verified.

The final analysis of all data collected in the study, including the extension period, will occur after all subjects have completed the study.

Details of the planned statistical analyses mentioned below in this section will be fully specified in the Statistical Analysis Plan, which will be finalized prior to the locking the study database.

All subjects who have received at least one dose of the study drug, whether prematurely withdrawn from the study or not, will be included in the safety analysis population. Data will be analyzed according to the expected treatment of 4 mg balovaptan. Any dosing error will be reviewed and the implications of such errors on safety interpretation will be assessed.

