3.1.3 Six-Week Treatment Period

All subjects will receive 6 weeks of treatment with an oral dose of 4 mg of balovaptan QD, which is predicted to be equivalent to the adult oral dose of 10 mg balovaptan QD. Study enrollment will occur only after a subject has met all eligibility criteria. At the baseline visit (Day 1), subjects will undergo a series of assessments outlined in the schedule of activities (see ).

The target exposure range for a 10-mg equivalent dose is based on the observed exposure distribution in adults receiving 10 mg balovaptan QD in Study BP28420, with a median $AUC_{\tau,ss}$ of approximately 1000 ng•hr/mL, interquartile range of approximately 700–1400 ng•hr/mL, and 90% of $AUC_{\tau,ss}$ values (5th–95th percentile) within approximately 400–2000 ng•hr/mL.

For the first subject, if the $AUC_{\tau,ss}$ is >2000 ng•hr/mL or <400 ng•hr/mL, then the dose will be adjusted with the aim to get $AUC_{\tau,ss}$ as close as possible to the target 1000 ng•hr/mL. Any new subject to be enrolled will receive this adjusted dose, unless cumulative data from all subjects in the study indicate that further dose adjustments are required to be within the target distribution. If required based on accumulating PK data,

the dose may be adjusted further. It is planned that any dose change will be implemented for all enrolled subjects and any additional enrolled subjects. However, if indicated based on large variability in the systemic exposure of balovaptan, different doses may potentially be given for children of different ages or adjustment of dose may potentially be done for a given individual subject so that plasma exposures are not outside the targeted range for an extended period of time. Subjects should come to the site for an unscheduled study visit as soon as possible after a dose change is confirmed if subjects cannot receive the new study drug supply at the next regular study visit early enough or if any other relevant clinical, administrative, or operational reasons call for an additional study visit. The decision to change the dose will be made by the Sponsor and communicated to sites.

If treatment interruption occurs between Day 1 and Week 2 (the PK sampling visit), after consultation with the clinical pharmacologist, subjects may need to be withdrawn and replaced or the Week 2 PK visit may be delayed.

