3.1.4 Optional Extension Period

All subjects who complete the 6-week treatment period, and in the view of the investigator, have not experienced relevant adverse events considered prohibitive for further treatment are eligible for participation in the extension period of the study. The transition into the extension period is seamless; subjects will continue to receive study drug treatment without interruption after the end of the 6-week period. Subjects who do not participate in the extension period of the study will complete the follow-up visit 2 weeks after their final dose (see Section 3.1.5).

The 48-week duration of the extension period serves to evaluate the long-term safety, tolerability, and exploratory efficacy of balovaptan treatment in young children with ASD. All subjects will continue to receive an oral dose of 4 mg balovaptan QD, which is predicted to be equivalent to the adult oral dose of 10 mg balovaptan QD. If a change in dose occurs, all subjects in the 6-week treatment period and all subjects in the extension period will receive the new dose at the earliest opportunity (see Section 3.1.3). For the schedule of activities to be performed during the extension period, see [REDACTED].

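### Section 6 fixes the analysis label at 4 mg although the protocol provides for planned dose changes, so safety summaries could carry the wrong dose

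*Combined protocol and SAP*

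**What the plan says.** Section 6 puts every child who received at least one dose in the safety population and continues: "Data will be analyzed according to the expected treatment of 4 mg balovaptan". The next sentence covers departures only in this form: "Any dosing error will be reviewed and the implications of such errors on safety interpretation will be assessed". Planned changes are not mentioned there. The same section says that analysis details "will be fully specified in the Statistical Analysis Plan, which will be finalized prior to the locking the study database".

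Other sections do not treat 4 mg as fixed:

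- **Section 3.1.3** requires an adjustment if the first child's steady-state AUC is above 2000 or below 400 ng·hr/mL, and allows more on accumulating data. On scope it says: "It is planned that any dose change will be implemented for all enrolled subjects and any additional enrolled subjects". It also allows that "different doses may potentially be given for children of different ages" and that "adjustment of dose may potentially be done for a given individual subject".
- **Section 3.1.4** says that after a change "all subjects in the extension period will receive the new dose at the earliest opportunity".
- **Section 4.2** assigns each child to the confirmed dose without naming a figure.
- **The Synopsis** (test product) provides further tablet strengths for use if the dose changes.
- **Section 6.4** foresees dose-adjustment recommendations for the extension.

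The safety objective in Section 2.2 is framed around the 10-mg-equivalent dose, not around 4 mg.

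**The concern.** Finding the dose for this age group is part of the primary objective, so a dose change is built into the design. The analysis sentence nevertheless attaches one dose to the data with no condition. The error sentence beside it does not help: Section 5.3.5.11 defines a medication error as accidental, and a change directed by the sponsor is not accidental.

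If the dose changed and the sentence were applied as written, adverse events, laboratory values, vital signs and ECG results that arose at another dose would be summarised under 4 mg. Section 3.3.3 says the results are meant to allow this age group into the Phase III programme, so readers of those tables will care which dose they describe.

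**Working it through.** The point rests on comparing sections, and no figure in the plan is disputed. Arithmetic serves only to show how likely a change is and how much data it would touch.

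**1. Chance that the first-subject trigger is met**

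Inputs (Section 3.1.3, adults on 10 mg in Study BP28420): median 1000, interquartile range 700–1400, 5th–95th percentile 400–2000 ng·hr/mL. The trigger limits equal the 5th and 95th percentiles, so the plan's own figures give 10% outside if 4 mg is on target and children have the adult spread.

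Log-normal check:

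- SD from the 5th–95th percentiles: ln(2000/400) / (2 × 1.645) = 0.489
- SD from the quartiles: ln(1400/700) / (2 × 0.6745) = 0.514
- P(above 2000) + P(below 400) at median 1000: 0.078 + 0.031 = 0.109 with SD 0.489; 0.089 + 0.037 = 0.126 with SD 0.514

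If the children's median were off target (multiples assumed, SD 0.489), the chance would be about 28% at 1.5 times the target, 50% at 2 times and 33% at half.

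With the median on target, 10 × 0.10 to 10 × 0.126, that is 1.0 to 1.3 of 10 children, would be expected outside 400–2000. Individual adjustment is optional, so this is not a probability of a change. Later changes of any kind add an unknown amount.

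**2. Share of treatment time at another dose, given one study-wide change**

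From the documents: about 10 children, up to 18 months (78 weeks) of recruitment, 6 weeks of treatment plus an optional 48 (54 in all). Assumed: ten equally spaced entry times t_i from week 0 to week 78 (every 78/9 = 8.67 weeks), no dropout, and a change that takes effect for everyone at week T after the first child's first dose. T = 4 to 6 assumes 2 to 4 weeks from the Week 2 pharmacokinetic visit to an implemented change.

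Child-weeks at 4 mg = sum over children of min(d_i, max(0, T − t_i)), where d_i is treatment length. The rest is at another dose.

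| T (weeks) | 6-week analysis, 60 child-weeks: at 4 mg | At another dose | Final analysis, all treated 54 weeks, 540 child-weeks: at 4 mg | At another dose |
|---|---|---|---|---|
| 4 | 4 | 93.3% | 4 | 99.3% |
| 6 | 6 | 90.0% | 6 | 98.9% |
| 26 | 18 | 70.0% | 52 | 90.4% |
| 52 | 36 | 40.0% | 182 | 66.3% |
| 78 | 54 | 10.0% | 344 | 36.3% |

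Example, T = 26: three children have started, each with at least 6 weeks behind them, so 3 × 6 = 18 child-weeks. In the final analysis they contribute 26 + 17.33 + 8.67 = 52.

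If only every second child enters the extension (5 × 54 + 5 × 6 = 300 child-weeks), the shares are 98.0–98.7% at T = 4 to 6, 86.4–90.2% at T = 26, 59.3–68.0% at T = 52 and 30.0–37.3% at T = 78. The ranges for T = 26 and later depend on which children continue.

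**The case against.** The best defence is that the sentence is shorthand. It speaks of expected treatment, and Sections 3.1.3 and 3.1.4 also state 4 mg flatly before providing for a change. Details are deferred to a separate SAP that is not in the file reviewed and that would be finalised before database lock, when any change up to the 6-week lock could be known. Part of Section 6.5 is redacted, and its next visible sentence lists examination findings by treatment, which could mean by dose.

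These points limit the finding. Whether the final tables would be mislabelled is uncertain, and the redacted text is not counted as missing. They do not rescue the sentence. If the assigned dose is meant, the sentence should say so. A SAP that followed it would mislabel data after a change, and a SAP that departed from it would contradict the protocol.

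It is also fair that the consequence is conditional and the child-week shares are scenarios. The highest shares arise where nearly all data are at the new dose, and there a 4 mg label is least likely to survive.

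Two objections to analysing by dose received carry some weight. Steady state takes about 7 days in healthy subjects (Section 1.2.2.3), so an event soon after a change may belong to the previous exposure. Events after the last dose have no current dose. Both are minor: attribution by dose at onset is conventional, and Section 6.5 already summarises follow-up data separately.

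**Conclusion.** The concern holds, and the plan should be corrected. What is certain is the conflict between an unconditional 4 mg rule in Section 6 and the planned dose changes in Sections 3.1.3 and 3.1.4. No visible text reconciles them.

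Wrong labels follow only if a planned change occurs and the sentence is applied literally. The first part is realistic: about 10% (10.9–12.6% with the log-normal fits) from the first-subject trigger alone, on the assumption that 4 mg is on target and children share the adult spread. Given a study-wide change, the share of treatment time affected runs from 10% to 93% in the 6-week analysis and from 30% to 99% in the final analysis, depending on the assumed timing and extension uptake.

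The damage is confined to summaries. Individual listings (Section 6.5) and the eCRF (Section 4.3.2) preserve the dose, the monitoring committees see all available data (Section 3.1.6), and the primary pharmacokinetic analysis is unaffected. A pooled total would still answer the safety objective, but under the wrong label. If the dose never changes, nothing is wrong.

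**What to change.** Reconcile Section 6 with Sections 3.1.3, 3.1.4 and 4.2. Replace the 4 mg sentence with a rule along these lines:

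- If any planned dose change occurs, summarise safety data descriptively by dose actually received. Place adverse events under the dose at onset and measurements under the dose at assessment.
- Report the number of children and the child-weeks of treatment at each dose.
- Add an all-doses total labelled as the 10-mg-equivalent regimen, not as 4 mg.
- Apply the rule at both the 6-week and the final analysis.

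If the SAP or the redacted part of Section 6.5 already has such a rule, only the Section 6 sentence needs to change. No dose is proposed here.

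The cost is one sentence, matched in the SAP, and extra table columns only if a dose changes. No new data are needed, because dose modifications are already recorded. The drawback is that some columns may hold only one to three children, and a child treated at two doses appears in both, so column counts will not add up to the total.

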6.1 DETERMINATION OF SAMPLE SIZE

The sample size required to determine the dose that will deliver adult-equivalent exposures in pediatric subjects was previously assessed for Study BP30153, based on a bootstrapping methodology combined with PBPK exposure simulations. With a sample size of 10 children, the 90% CI for the apparent CL estimate was 74%–130% of the true apparent CL for the age group of 5- to 7 year old children, indicating that the derived adult-equivalent dose would result in exposures within approximately 30%–40% of the target exposure (Methodology to Guide Pediatric Dose Adjustments and Determine the Sample Size for Early PK Assessment in Adolescents and Children based on PBPK information. Report 1093374, February 2016).

As the variability in apparent CL is expected to be similar in 2- to 4-year old children as in 5- to 17-year olds (PBPK modeling Report 1084465), the same sample size was assumed appropriate.

The primary CL mechanism of balovaptan is metabolism via CYP3A4 (producing M1, M2, and M3) and to a minor extent by means of CYP2D6 (producing M4). In humans, these systems are known to attain adult capacity per gram of liver tissue in the first few years of life as shown by in vitro enzyme expression data as well as based on clinical pharmacokinetics for known substrates (Salem et al. 2014). In children aged 8–17 years, it has been confirmed that no dose adjustment is required in order to achieve similar

exposures as in adults, whereas in children ages 5–7 years, a reduction in CL of approximately 35% was detected. Approximately 10 subjects treated with active drug in the various age groups in Study BP30153 (8–11 years, 12–14 years, and 15–17 years) have shown to be sufficient to determine the dose that provides equivalent exposure as observed in adults treated with 10 mg with adequate precision.

6.2 SUMMARIES OF CONDUCT OF STUDY

The number of subjects who enroll, discontinue, or complete the study will be summarized. Reasons for premature study withdrawal will be listed and summarized.

6.3 SUMMARIES OF DEMOGRAPHIC AND BASELINE CHARACTERISTICS

Demographic (including age and sex) and baseline characteristics will be summarized using means, standard deviations, medians, and ranges for continuous variables, and proportions for categorical variables, as appropriate.

6.4 PHARMACOKINETIC ANALYSES

Individual and mean plasma concentration data per timepoint will be listed for the parent and metabolite and the ratio of metabolite to parent concentration will be derived.

Nonlinear mixed-effects modeling will be used to analyze the sparse sampling dose-concentration-time data collected for balovaptan. A previously developed pop-PK model will be used to analyze the PK data in this study. Population and individual PK parameters will be estimated and $AUC_{\tau,ss}$ derived from the individual PK model parameter estimates. The dose resulting in an adult-equivalent exposure will be calculated from the ratio of apparent CL estimates in 2- to 4- year-old children to apparent CL in adults.

The results of the pop-PK model based analyses may be reported in a document separate from the clinical study report.

Exposure equivalence with adult exposures after QD dosing with age-adjusted 10-mg dose of balovaptan will be confirmed, and if needed, dose-adjustment recommendations will be made for subjects continuing in the extension period.

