For the first subject, if the $AUC_{\tau,ss}$ is > 2000 ng•hr/mL or < 400 ng•hr/mL, then the dose will be adjusted with the aim to get $AUC_{\tau,ss}$ as close as possible to the target 1000 ng•hr/mL. Any new subject to be enrolled will receive this adjusted dose, unless cumulative data from all subjects in the study indicate that further dose adjustments are required to be within the target distribution. If required based on accumulating PK data, the dose may be adjusted further. It is planned that any dose change will be implemented for all enrolled subjects and any additional enrolled subjects. However, if indicated based on large variability in the systemic exposure of balovaptan, different doses may potentially be given for children of different ages or adjustment of dose may potentially be done for a given individual subject so that plasma exposures are not outside the targeted range for an extended period of time. Subjects should come to the site for an unscheduled study visit as soon as possible after a dose change is confirmed if subjects cannot receive the new study drug supply at the next regular study visit early enough or if any other relevant clinical, administrative, or operational reasons call for an additional study visit. The decision to change the dose will be made by the Sponsor and communicated to sites.

If treatment interruption occurs between Day 1 and Week 2 (the PK sampling visit), after consultation with the clinical pharmacologist, subjects may need to be withdrawn and replaced or the Week 2 PK visit may be delayed.

Optional Extension Period

All subjects who complete the 6-week treatment period, and in the view of the investigator, have not experienced relevant adverse events considered prohibitive for further treatment are eligible for participation in the extension period of the study. The transition into the extension period is seamless; subjects will continue to receive study drug treatment without interruption after the end of the 6-week period. Subjects who do not participate in the extension period of the study will complete the follow-up visit 2 weeks after their final dose.

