3. STUDY DESIGN

3.1 DESCRIPTION OF THE STUDY

This is a Phase Ib, multicenter, open-label study in children 2–4 years old with ASD to investigate the pharmacokinetics, safety, and tolerability of an oral dose of 4 mg balovaptan QD, which is predicted to *be adult-equivalent, i.e., provide a plasma exposure range that is comparable to that following oral doses of 10 mg balovaptan QD in adults*. The study consists of a 6-week treatment period to evaluate the pharmacokinetics of balovaptan in 2- to 4-year old children followed by an optional extension period of 48 weeks.

Subjects for whom consent has been provided by their parent or legal guardian will undergo screening within 4 weeks prior to the first study drug administration. Eligible subjects will be enrolled in an open-label fashion and treated with 4 mg balovaptan.

The safety of balovaptan will be assessed by monitoring of adverse events, serious adverse events, clinical laboratory values, ECGs, physical and neurologic examinations, and safety outcome assessments such as suicidality. Exploratory efficacy endpoints will examine core autism symptoms (social interaction, social communication) and functional deficits.

The total duration of the study (from screening through to study completion) for each subject will be approximately 12 weeks or 60 weeks, depending on whether or not he or she participates in the optional extension period, divided as follows:

[figure not shown]
- Screening period: approximately 4 weeks
- Treatment period: 6 weeks
- Optional extension period: 48 weeks
- Post-treatment follow-up period: 2 weeks

Approximately 10 subjects will be enrolled at approximately 10 international sites, including sites in North America and Spain. A subject may be replaced in the event that the subject's treatment is discontinued for any reason during the 6-week treatment period.

Enrollment will be based on the selection of two age groups (children 3–4 years old vs. children 2 years old). The targeted ratio between the age groups will be approximately 2:1 (children 3–4 years old to children 2 years old; e.g., 7 children 3–4 years old and 3 children 2 years old if 10 subjects are enrolled). This ratio may change based on the ability to recruit children in both age groups and based on observed exposures levels of balovaptan and its metabolites.

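### Does Section 6.4 need a stated equivalence criterion before it can say that children's exposure matches adults'?

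*Combined protocol and SAP*

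**What the plan says.** Section 6.4, repeated in the Synopsis under Statistical Methods, plans a mixed-effects analysis with an existing pop-PK model, individual steady-state AUCs, and a dose derived from clearance: "The dose resulting in an adult-equivalent exposure will be calculated from the ratio of apparent CL estimates in 2- to 4- year-old children to" the adult value. It then says "Exposure equivalence with adult exposures after QD dosing with age-adjusted 10-mg dose of balovaptan will be confirmed", and continues "and if needed, dose-adjustment recommendations will be made for subjects continuing in the extension period".

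The reference for that comparison stands elsewhere. Section 3.1 explains an adult-equivalent dose as one predicted to "provide a plasma exposure range that is comparable to that following oral doses of 10 mg balovaptan QD in adults". Section 3.1.3 gives the adult distribution at 10 mg QD: a median AUC of about 1000 ng•hr/mL, "interquartile range of approximately 700–1400", and 5th to 95th percentiles of about 400–2000. The limits 400 and 2000 are attached explicitly to the first child. After that, "If required based on accumulating PK data, the dose may be adjusted further" (Synopsis and Section 3.1.3).

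Section 6.1 states the expected precision. With 10 children, "the 90% CI for the apparent CL estimate was 74%–130% of the true apparent CL", a result simulated for ages 5–7 in Study BP30153. Section 6 says that analysis details "will be fully specified in the Statistical Analysis Plan, which will be finalized prior to the locking the study database". No separate SAP is among the documents supplied.

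**The concern.** To confirm equivalence normally means showing that an interval lies inside limits set in advance. Section 6.4 has neither interval nor limits. It does not say whether a mean, an interval or the individual AUCs are to be judged, or against which of the Section 3.1.3 ranges. The timing adds to the worry. The SAP need only be final before database lock, which for the 6-week analysis comes after the last Week 6 assessment. By then the Sponsor will have reviewed accumulating PK results and may have changed the dose on them, in an open-label study.

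If this were a real defect, the same 10 children could be reported as confirmed or not confirmed depending on a rule chosen afterwards. That statement bears on the dose recommendations for the extension and, under Sections 3.3.1 and 3.3.3, on taking this age group into later trials.

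**Working it through.** **1. The plan's own precision figure.** Inputs: 74%–130% and n = 10 (Section 6.1); adult percentiles (Section 3.1.3).

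- Log half-width: (ln 1.30 − ln 0.74)/2 = 0.2817.
- Standard error: 0.2817/1.645 = 0.171.
- Implied log-SD for n = 10: 0.171 × √10 = 0.542 with the normal quantile, or 0.2817/1.833 × √10 = 0.486 with t on 9 df.
- Adult log-SD, if AUC is log-normal: ln(2000/400)/(2 × 1.645) = 0.489, or ln(1400/700)/(2 × 0.6745) = 0.514.
- Forward check, exp(±q × SD/√10): the normal quantile gives 77.5%–129.0% (SD 0.489) and 76.5%–130.6% (SD 0.514); t gives 75.3%–132.8% and 74.2%–134.7%.

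The printed interval agrees with 10 children and adult-like variability. The simulation behind it cannot be rerun from the documents.

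**2. What that precision means for exposure.** A dose set from the estimated clearance gives a true exposure of target × (estimated CL/true CL), so 740–1300 against a target of 1000. Read the other way, an AUC estimated at one fixed dose varies as 1/CL: 1000/1.30 = 769 to 1000/0.74 = 1351. Both fit the 30%–40% stated in Section 6.1. The predicted child-to-adult clearance ratio is 4/10 = 0.40, which would carry about 0.40 × 0.74 = 0.30 to 0.40 × 1.30 = 0.52. A reader of the protocol can already see how far typical exposure might lie from target.

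**3. What would happen if a formal criterion were read in.** The table gives the probability that a t-based 90% CI for the child-to-adult exposure ratio lies inside the limits. It assumes n = 10, log-normal AUC, a fixed adult value and log-SD from 0.486 to 0.542, with 400,000 simulated trials per SD.

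| Limits read in | True ratio 1.0 | True ratio 1.3 |
|---|---|---|
| 0.80–1.25 | 1.8–3.8% | 0.6–0.9% |
| 0.70–1.40 (adult quartiles) | 23.7–36.4% | 7.9–10.2% |
| 0.40–2.00 (adult 5th–95th) | 98.0–99.4% | 75.0–82.7% |

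Counting children inside 400–2000 also discriminates weakly. At least 8 of 10 fall inside with probability 83–92% at a true ratio of 1.0 and 59–69% at 1.3.

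These figures are correct under their assumptions, but they describe rules that are not in the plan. The margin 0.80–1.25 and the 8-of-10 count appear nowhere in the documents. The adult quartiles and outer percentiles describe spread between people, so using them as limits for the interval of a mean mixes two quantities. The results also move with the assumptions. If the adult mean is itself estimated from an assumed 30 adults (log-SD 0.489), the first row at a true ratio of 1.0 falls from 3.6% to 0.1% and the second from 35% to 21%.

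**4. Which outputs depend on the missing rule.**

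- AUC estimates (primary endpoint, Section 2.1): no.
- Adult-equivalent dose: no. It is 10 mg × (child CL/adult CL). Because AUC = dose/CL, dose changes during the study do not disturb it, and the AUC ratio at any common dose is the inverse of the CL ratio times a constant.
- Dose decisions while the study runs: no. These fall under Section 3.1.3.
- The summary sentence in the report, and whether an extension recommendation is thought to be needed: yes, but the estimates behind both are reported.

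**The case for a change.** The strongest case for a change is that the sentence is worded as a conclusion, and that whether a recommendation is needed turns on the same undefined judgement. A SAP finalised just before lock would let that judgement be formed with the exposures already seen and no blinding to guard it. The repair would also be cheap: an interval, a cross-reference and a softer verb.

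Part of this stands. Section 6.4 has no interval, no pass rule and no cross-reference, and the verb is stronger than 10 children could support under a narrow margin.

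The rest goes too far. Database lock is the latest date for the SAP, not its planned date, so late setting of a rule is a possibility and not something the plan prescribes. The reference distribution is numeric and fixed in the protocol, so only the manner of comparison is open. The protocol uses the same verb loosely elsewhere: Section 3.3.1 speaks that way of the expected exposure, and Section 6.1 of the finding in ages 8–17. The sentence here goes straight on to what happens if exposures do not match. Asking for both an AUC ratio at a common dose and a CL ratio, each with an interval, would give essentially one result twice. Softer wording would supply no criterion either.

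**Conclusion.** This is a gap in detail, and analysts can be expected to fill it sensibly. Population estimates from a mixed-effects model ordinarily come with their uncertainty, so an interval on the clearance ratio is a routine output, and the adult distribution to set the individual AUCs against is already printed. The dose calculation and the primary endpoint are unaffected. The expected precision, 74%–130%, is disclosed and agrees with the adult spread.

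The pass rates, from 2–4% to 98–99% when exposures truly match, show only that a formal test would depend heavily on its margin. The plan names no such test. Those rates rest on reviewer-chosen limits, log-normal AUC, a simple t-interval in place of the pop-PK model, and an adult value treated as known.

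The conclusion assumes that the separate SAP, which was not available, does not turn the sentence into a formal equivalence test with limits chosen after the exposures are seen. Nothing in the protocol says that it will. No change to the plan is called for.
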